### Assessments

#### *Impromptu Speech Behavioral Assessment Test*

The impromptu speech BAT will be performed 1 hour after the subject receives study medication as outlined in the table below (26-28). Participants will be asked to speak about pre-determined topics for 10 minutes to a small audience of research staff

(27). Patients with more severe social anxiety symptoms are often not able to speak for the full 10 minutes and have shorter speech lengths when compared to those with less severe social anxiety symptoms (26-28). VAS-anxiety, State-Trait Anxiety Inventory and the Self-Statement during Speech Test (SSPS) (28) will be assessed before and after the speech. The Local Tolerability Assessment (Appendix 1) will be performed at screening, baseline, 1 hour after receiving the study medication and before discharge.

The Table below shows the assessment schedule for participants enrolling in the trial.

Measure	Screening	Challenge DAY 1					2-10 day washout period	Challenge DAY 2					2-10 days	Follow up visit
		Baseline	0	1h	2h	3h		Baseline	0	1h	2h	3h		
Local Tolerability Assessment	X	X		X		X		X		X		X		
Impromptu Speech Task				X					X					
VAS-anxiety	X	X	X	X	X	X		X	X	X	X	X		
VAS-speech performance				X					X					
SSPS		X		X				X	X					
STAI		X		X				X	X					
DSST		X		X				X	X					
Immediate and Delayed Word Recall		X		X				X	X					
Clinical-rated VAS-anxiety				X					X					
Clinician rated VAS-speech performance				X					X					
LSAS	X	X						X						
SCID	X													
C-SSRS	X					X						X		
Physical Exam with Vital signs (BP, HR: supine, standing X 2-3 min) and Visual exam of the oral cavity	X	X				X		X				X		X
Blood test	X													X
Urine Test	X	X						X						
EKG	X													
STUDY MEDICATION ADMINISTRATION			X						X					

The rating scales utilized in the trial are detailed in the table below. Ratings will be conducted by raters that are blinded to treatment assignment and will not be present during medication administration.

- RATING SCALES:**
- 1) *Visual Analog Scale (VAS) of Anxiety States:* The VAS includes scales for anxiety, drowsiness, high, irritability, anger, and sadness. These scales are 100 mm lines marked by participants at a point corresponding to the apparent intensity of the feeling state (0=none, to 100=most ever) (29). We will also use clinician-rated visual analogue scales to measure subject anxiety and speech performance during the Impromptu Speech Task.
  - 2) *Self-Statement During Public Speaking Scale (SSPS):* The SSPS is a rating scale used to measure cognitions that occurred during a speech (28).
  - 3) *State-Trait Anxiety Inventory (STAI):* The STAI is a standardized rating scale of trait and state anxiety (30).
  - 4) *Digit Symbol Substitution Task (DSST):* Digit Symbol Substitution Tasks requires the subject to match symbols with their corresponding digit. It consists of 9 digit symbols matched with their corresponding numerical digit. Subjects are asked to match as many number-symbol pairs within a 90 second time limit. Performance

of the DSST has been demonstrated to be impaired by acute treatment with benzodiazepines (31).

- 5) Immediate and Delayed Word Recall Test – In this task, a list of 10 words will be repeated 3 times to subjects at a pace of 1 word every 2 seconds. Immediately after presentation of the list and 5 minutes later subjects will be asked to recite as many of the words as they can from memory. Performance on this task has been demonstrated to be impaired by acute treatment with benzodiazepines (31).
- 6) Local Tolerability Assessment: Systematized oral cavity inspection checklist (Appendix 1).
- 7) Columbia-Suicide Severity Rating Scale (C-SSRS) – Assessment of suicidal ideation and behavior in clinical and research settings(25)

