- Each subject will be given BHV-0223 (or placebo) under double-blind conditions 1-hour before performing the impromptu speech task on 2 separate study days.
- There will be a 2 to 10 day washout period between study days.
- There will be a final Follow-up visit 2 to 10 days later to do blood work and complete physical exam.

Overview:

We propose conducting a double-blind, placebo controlled crossover study examining the effects of BHV-0223 on public speaking anxiety. Twenty subjects with DSM-5 defined social anxiety disorder and clinically significant public speaking anxiety on the Impromptu Speech Task will be enrolled in a challenge study. Subjects will be given BHV-0223 (or placebo) under double-blind crossover conditions 1 hour prior to performing each of 2 impromptu speech tasks. The two study days involving BHV-0223 (or placebo) administration and impromptu speech task will be separated by 2 to 10 days to allow for medication washout. There will be a final follow-up visit 2 to 10 days later to perform a complete Physical exam and do follow-up liver function testing and a Complete Blood Count. Our primary outcome will examine BHV-0223's effects (compared to placebo) on self-rated anxiety during the impromptu speech task. We will also collect physiological measures of anxiety, clinician-rated measures of anxiety, and measures of speech performance as secondary outcomes.

Screening:

A baseline screening assessment to determine study eligibility, clinical ratings, and physical health will be conducted at least one week prior to the challenge study.

*Medical Assessments*

During the screening visit, vital signs (BP, HR: supine, standing X 2-3 min), physical exam (including a comprehensive exam of the oral cavity see Appendix 1), and clinical laboratory tests (i.e. CBC with differential, complete metabolic panel (CMP) (including electrolytes, LFTs, BUN, creatinine and glucose), TFTs, urine drug screen, and routine urinalysis) will be completed. A pregnancy test will be given to all females of childbearing age enrolled in the study prior to participating in the study sessions. We will also perform a visual inspection of the mouth cavity to assess local tolerability before and 1 hour after administering study medication on each study day (please see appendix document for further details).

*Psychiatric Assessments*

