## Statistical Analyses

Assuming that there are no ordering or period effects in the trial, we will use a paired t-test to compare ratings of anxiety during the impromptu speech task after BHV-0223 vs. placebo treatment. Given a sample size of 20 subjects, assuming a one-sided  $\alpha=0.1$ , we would have 80% power to detect a treatment effect size=0.5 or greater. As a comparison previous studies of benzodiazepines have demonstrated an effect size of at least 0.9 on similar speech paradigms (32). Our primary measure will be the VAS-anxiety after the impromptu speech task (BHV-0223 compared to placebo). As additional secondary measures we will collect (1) subject ratings of speech performance, self-statements during public speaking (SSPS) and specific anxiety symptoms during speech (STAI); (2) clinical ratings of speech performance; (3) duration of speech; (4) assessments of cognition – (DSST and 15 word recall) and 5) side-effects.

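### The schedule table puts the Day 2 speech in the dosing column, against the text's 1 hour after dosing on both days; separately, the primary VAS-anxiety reading is not tied to one mark.

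*Combined protocol and SAP*

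**What the plan says.** The text of Section V.3 gives one interval for both days. The Overview states: "Subjects will be given BHV-0223 (or placebo) under double-blind crossover conditions 1 hour prior to performing each of 2 impromptu speech tasks". The summary bullets of the Research Plan say the same for the two study days. The paragraph on the Impromptu Speech Behavioral Assessment Test repeats it and points to the schedule: "The impromptu speech BAT will be performed 1 hour after the subject receives study medication as outlined in the table below".

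The speech row of that schedule, "Impromptu Speech Task X X", has two marks. As extracted, the first is under 1h of Challenge Day 1 and the second under 0 of Challenge Day 2. The row "STUDY MEDICATION ADMINISTRATION" is marked under 0 on both days. The row "VAS-anxiety X X X X X X X X X X X" is marked at screening and then at baseline, 0, 1h, 2h and 3h on each challenge day.

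The same section says that VAS-anxiety, the STAI and the SSPS "will be assessed before and after the speech". It also says that raters are kept away while study medication is given.

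Under Statistical Analyses, the primary measure is defined by the speech and not by a column: "Our primary measure will be the VAS-anxiety after the impromptu speech task (BHV-0223 compared to placebo"). The test is given as "Assuming that there are no ordering or period effects in the trial, we will use a paired t-test", and that sentence describes the ratings as made *during* the speech.

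**The concern.** The table that the text cites for the timing of the speech shows a different timing on Day 2. The documents do not say whether text or table governs, and staff commonly work from a schedule table on the day. If they worked from this one, the speech would come 1 hour after dosing on Day 1 and at dosing on Day 2. Subjects who receive BHV-0223 second would then speak with little or no time for absorption, while those who receive it first would have an hour. That is a period difference built into the schedule, in a trial whose primary test assumes there is none. Once the ratings are taken, they cannot be moved to a common interval.

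The second question is which VAS-anxiety mark is the primary value. With five marks on each challenge day and no time label, two analysts could choose different ones.

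**Working it through.** **1. Text against table.** Each extracted row has 15 cells, so marks can be matched to the column headings by position.

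| Item | Day 1 | Day 2 |
|---|---|---|
| Text: speech | 1 hour after dosing | 1 hour after dosing |
| Table: study medication | 0 | 0 |
| Table: speech | 1h | 0 |
| Table: VAS-speech performance | 1h | 0 |
| Table: SSPS, STAI, DSST, word recall | baseline, 1h | baseline, 0 |
| Table: both clinician-rated VAS rows | 1h | 0 |
| Table: VAS-anxiety | baseline, 0, 1h, 2h, 3h | baseline, 0, 1h, 2h, 3h |
| Table: local tolerability | baseline, 1h, 3h | baseline, 1h, 3h |

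Eight rows shift: 1 (speech) + 1 (VAS-speech performance) + 4 (SSPS, STAI, DSST, recall) + 2 (clinician-rated VAS) = 8. VAS-anxiety and local tolerability do not shift.

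**2. Could it be a reading error?** No cell was dropped, since the rows are complete. In the four rows that also have a baseline mark, the Day 2 baseline mark is where it should be and only the next mark is one column early. Local tolerability keeps its Day 2 1h mark. A fault confined to the speech-linked rows is unlikely, but a misplaced mark within a complete row cannot be excluded without the original PDF.

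**3. Which reading is primary?** On Day 1 the speech and a single VAS-anxiety mark share the 1h column. That mark could be taken before or after the speech. The baseline and 0 marks also precede the speech, and the 2h mark also follows it. Statistical Analyses uses both *during* and *after*. Nothing names the mark. This holds on Day 1 alone, so correcting Day 2 would not remove it.

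**4. The plan's power, reproduced.** Inputs from Statistical Analyses: n = 20, effect size d = 0.5, one-sided alpha 0.10, stated power 80%. For a paired t-test, power = P(T > t(0.90; 19)), with T noncentral t on 19 degrees of freedom and noncentrality d√n = 0.5 × √20 = 2.236. The critical value is 1.328 and the power 0.817, which agrees with the stated 80%.

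Section V.12 gives d = 0.58 and alpha 0.05 with no side stated. Taken as one-sided, the power is 0.804, which also agrees.

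**5. Size if the table were followed.** Assumptions, not in the documents: 10 subjects per order; the planned effect holds at 1 hour; a speech given at dosing shows a fraction f of it, from 0 to 0.5. The mean paired effect is then d(1 + f)/2. For d = 0.5:

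- f = 0.5: 0.5 × 1.5/2 = 0.375
- f = 0: 0.5 × 1/2 = 0.25

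Power, simulated with 10 differences from N(d, 1) and 10 from N(fd, 1) and a one-sample t-test on all 20:

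| Plan figures | f = 1 | f = 0.5 | f = 0 |
|---|---|---|---|
| d = 0.5, one-sided 0.10 | 0.82 | 0.64 | 0.41 |
| d = 0.58, one-sided 0.05 | 0.80 | 0.58 | 0.32 |

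**6. The interim look.** Section V.12 treats an estimated effect below 0 after 10 subjects as a reason to stop. With 5 per order and d = 0.5, the chance of this is Φ(−0.5 × (1 + f)/2 × √10):

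- f = 1: Φ(−1.581) = 5.7%
- f = 0.5: Φ(−1.186) = 11.8%
- f = 0: Φ(−0.791) = 21.5%

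**The case against.** The best reply is that the text settles the matter. It states the interval three times without conflict, the primary measure is tied to the speech and not to a column, and the VAS-anxiety row is the same on both days. A like-for-like reading after the speech can therefore be taken on each day. The rule that keeps raters away from dosing also fits badly with clinician ratings in the dosing column, and that too points to a slip in the table.

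Most of this stands. A reader might infer from the table that the primary outcome has no common occasion on the two paired days, or that the Day 2 speech is planned at dosing. The documents support neither inference, for the reasons just given. Nor does the column mismatch cause the uncertainty about the primary reading, which is present on Day 1 by itself.

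Two things survive the reply. The sentence that fixes the interval relies on a table that contradicts it, and the text nowhere says which VAS-anxiety mark is the primary one.

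**Conclusion.** The table and the text of Section V.3 contradict each other on the Day 2 timing of the speech and of seven linked assessments. The passages must be reconciled. A clerical error in the table is the most likely explanation, subject to a check of the original PDF.

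The fall in power (0.82 to 0.41–0.64, or 0.80 to 0.32–0.58 on the Section V.12 figures) and the higher chance of a negative interim estimate (5.7% to 11.8–21.5%) are conditional. They need staff to follow the table against the text, and they rest on assumed balanced orders and an assumed 0 to 50% effect at dosing. They show what the error could cost; they are not a forecast. If the text is followed on both days, the loss is nil.

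Separately, the primary VAS-anxiety value is not tied to one reading on either day. That gap does not depend on how the table is read.

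**What to change.** Check the original table, then reconcile its Day 2 columns with the text so that the dose-to-speech interval, and the timing of the linked assessments, is the same on both days.

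Name one primary value per day: the first self-rated VAS-anxiety after the speech ends, including when the subject stops early. Show it in the table separately from the pre-speech reading, and use the same term for it throughout Statistical Analyses and Section V.12.

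The cost is a correction to eight table rows, one split mark in the VAS-anxiety row and one or two sentences. No visit, procedure or subject is added. Recording the clock times of dosing, end of speech and VAS mark would allow the interval to be verified, but is optional.

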The SCID (Structured Clinical Interview for DSM disorders) on the screening day to verify presence of social anxiety disorder and the absence of other psychiatric conditions (psychotic disorders, current substance abuse/dependence etc.). The *Liebowitz Social Anxiety Scale (LSAS)* will be administered to determine that public speaking anxiety symptoms are significant enough for inclusion in the trial. The LSAS is a rating scale that assesses SAD severity (21) and a 5-item subscale rates public speaking fear (22). Psychiatric rating scales examining the severity of anxiety (*Hamilton Anxiety Rating Scale (HAM-A)* (23)) and depressive symptoms *Hamilton Depression Rating Scale (HAM-D)* (24) will also be administered. Per FDA guidelines, suicidal ideation and behavior will be monitored using the C-SSRS(25) at screening and on every visit day.

Intervention:

Subjects will be given BHV-0223 35mg or placebo in a random order as assigned through the CMHC pharmacy with a 2 to 10 day separation between task days. Randomization will be performed by the CMHC pharmacy. The identity of the treatments will be concealed by the use of study drugs that are identical in packaging, labeling, schedule of administration and appearance. Placebo and study drug will be prepared in a like fashion in the CMHC pharmacy. Unblinding of a specific patient's randomization assignment will only occur during the study in the case of specific patient emergencies.

BHV-0223 is a sublingual, oral-disintegrating tablet containing 35mg of riluzole drug substance. BHV-0223 35mg tablets have shown bioequivalence to riluzole 50mg administered orally (please see PIND 128411 for further details). The half-life of BHV-0223 is just under 8 hours. Riluzole is a member of the benzothiazole class of medications. Chemically, its molecular formula is  $C_8H_5F_3N_2OS$  and its molecular weight is 234.2. The efficacy of riluzole in the treatment of ALS was established in two well-controlled studies. Patients randomized to treatment with riluzole showed longer time to tracheotomy or death compared to those treated with placebo. The recommended dose of riluzole in the treatment of ALS is 50mg taken every 12 hours (at least an hour before, or two hours after, a meal to avoid food-related decreases in bioavailability). Riluzole's mechanism of action in the treatment of ALS is unknown but thought to be due to its down-modulation of glutamatergic neurotransmission.

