### **Safety Data from the Phase 1 Study BHV223-101**

There were no drug-related SAEs reported in BHV-223-001. Additionally, no patients discontinued treatment due to drug-related AEs. BHV-0223 had good mouth palatability with expected mild and transient oral paresthesias. The vast majority of subjects rated the oral parathesias as mild and not bothersome, with few patients considering the numbness to be “somewhat” bothersome. The PI deemed all cases of paresthesias as mild. All cases of oral parathesias were transient and resolved. Overall, the preliminary results suggest that the SL formulation of riluzole is well tolerated and associated with mild, transient and not bothersome oral paresthesias. The Sponsor believes that the potential safety benefits on hepatic function, ease of administration for patients with dysphagia and potential to avoid the negative food effect associated with the generic tablet formulation outweigh any mild and transient oral numbness associated with the API.

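### Could the oral tolerability check at 1 hour prompt subjects about a drug-linked mouth sensation just before they give the primary anxiety rating?

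*Combined protocol and SAP*

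**What the plan says.** Three places in the combined protocol and SAP put an oral check 1 hour after dosing.

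- Section V.3, Assessments: "The Local Tolerability Assessment (Appendix 1) will be performed at screening, baseline, 1 hour after receiving the study medication and before discharge".
- Section V.3, Screening (Medical Assessments) plans a "visual inspection of the mouth cavity to assess local tolerability before and 1 hour after administering study medication on each study day".
- Appendix 1 lists baseline and 1 hour on both study days. Its content includes any history of burning or tingling in the mouth, followed by a systematic examination.

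The Assessments text sets the speech at the same 1-hour mark. The only order it gives around the speech is that VAS-anxiety, STAI and SSPS are taken before and after it. The Overview says the primary outcome concerns the drug's effect "on self-rated anxiety during the impromptu speech task", and Statistical Analyses names the VAS-anxiety score after the speech as the primary measure. The subject marks that scale.

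On blinding, Section V.3, Intervention, promises "study drugs that are identical in packaging, labeling, schedule of administration and appearance". Taste and mouth sensation are not mentioned. The Phase 1 safety summary in Section VI.A.2 reports that "BHV-0223 had good mouth palatability with expected mild and transient oral paresthesias" and refers to "any mild and transient oral numbness associated with the API". It adds: "The vast majority of subjects rated the oral parathesias as mild and not bothersome".

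**The concern.** Each subject takes both tablets and can compare the two days. If the active tablet tingles and the placebo does not, a question about tingling put just before the anxiety rating could tell the subject which day is which. A subject who believes the drug was given might then rate anxiety lower. Blinded raters who are absent at dosing cannot protect an outcome that the subject marks.

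Because the order is not written down, staff could follow the plan to the letter and still ask at the worst moment. They could also use different orders for different subjects, or on one subject's two days. With 20 subjects and a one-sided test, a small systematic shift in favour of the drug would raise the false-positive rate, and no later analysis could remove it.

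**Working it through.** **1. Is the order fixed anywhere?** No. Medical Assessments, Assessments and Appendix 1 all give 1 hour for the check, and Assessments gives 1 hour for the speech. The row order of the schedule table is not a sequence. The table's Day 2 speech column does not line up with the text as extracted and cannot be relied on. The plan therefore permits the check before the speech, between speech and rating, or after both.

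**2. What is the instrument?** The rating-scale list calls it an oral cavity inspection checklist, and Medical Assessments calls it a visual inspection. The recording form in Appendix 1 has mouth areas and mucosal grades but no symptom field. Appendix 1 does name symptoms, so some questioning is possible at 1 hour, but how prominent it would be is left open.

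**3. How new is the prompt?**

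- By the schedule table: 1 at screening + 2 days × 3 (baseline, 1 hour, 3 hours) = 7 assessments. Met before the 1-hour check: 2 on Day 1 (screening, baseline) and 2 + 3 = 5 on Day 2.
- By Appendix 1: 2 days × 2 = 4 assessments. Met before: 1 on Day 1 and 3 on Day 2.

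Reordering moves 2 of 7, or 2 of 4. The table also has a separate row for a physical examination with visual oral examination, at screening, baseline and 3 hours on each day, and follow-up: 1 + 2 × 2 + 1 = 6 further occasions.

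**4. Which cues would remain?** Any sensation felt while the sublingual tablet dissolves; the baseline check on the same day; and the VAS set itself, which includes items for feeling high and for drowsiness and, if given in full, is completed before the speech as well as after it.

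**5. What would reordering cost?** The check would follow a speech of up to 10 minutes and the ratings. With an assumed 5 to 15 minutes of ratings, the time after dosing is 60 + 10 + 5 = 75 to 60 + 10 + 15 = 85 minutes, against 60 minutes stated in three places. A transient local effect could be missed.

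**6. Can the bias be sized?** Not from the documents. The plan's power figure does not depend on the order: for a paired t-test with n = 20, df = 19 and one-sided α = 0.10, an effect of 0.5 gives noncentrality 0.5 × √20 = 2.236 and power 81.7%, against 80% stated.

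The same formula shows how far a result depends on guesses. Let the shift be the share of subjects who recognise the active day only because of the question, times their change in SD of the paired difference. With no true effect:

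| Assumed share × change | Shift | Noncentrality | Rejection at one-sided 0.10 | at one-sided 0.05 |
|---|---|---|---|---|
| none | 0 | 0 | 10.0% | 5.0% |
| 5% × 0.2 | 0.01 | 0.045 | 10.8% | 5.5% |
| 10% × 0.2 | 0.02 | 0.089 | 11.6% | 6.0% |
| 20% × 0.4 | 0.08 | 0.358 | 17.6% | 9.7% |

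Every share and every change is assumed, and nothing in the documents favours one row, including the first. The table describes the t-test, not this trial, and should carry no weight.

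**The case for a change.** The best case for acting is that the remedy is one sentence, it protects a self-rated primary outcome, and it cannot be applied after the data are in. The 1-hour check is the first scheduled oral check after dosing on each day, so it is the first that could tie a sensation to that day's tablet. The screening and Day 1 baseline checks come before any dose and cannot do that. N, α and power would stay as they are, and the 3-hour check would still follow.

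Most of this stands as description. The order is missing, the sensation is drug-linked by the protocol's own account, and fixing one order for both days is sensible practice. What does not stand is the step from there to a defect. For the prompt to matter, the sensation must still be present at 1 hour, must not have been noticed already, must be recognised because of the question alone, and must then move the rating in one direction. The documents support none of these links. They call the paresthesia transient and say it resolved. The blinding list does not mention sensation, but that does not show the placebo differs. Noticing an odd sensation might also raise anxiety instead of lowering it.

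**Conclusion.** No change to the plan is needed. This is a missing operational detail, of a kind staff normally settle on a visit worksheet, and the plan as written already allows the safer order. The effect on the primary comparison is of unknown size and direction and may be zero. Reordering would remove only part of the cueing and would push a safety observation later than its stated time, so a net gain is not shown in this 20-subject proof-of-concept study.

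Two clarifications are optional. The sponsor could state one order for both challenge days, with any symptom questions after the post-speech self-ratings if that suits safety monitoring. The sponsor could also reconcile the number of assessments, which is 7 per subject by the schedule table and 4 by Appendix 1.

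The conclusion assumes that no information outside these documents shows a marked difference in mouth sensation between drug and placebo lasting to 1 hour. If such information existed, blinding itself would be the issue, and the order of the check a minor part of it.
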